6.4.9. Liver chemistry stopping and follow up criteria

Liver chemistry stopping and follow up criteria have been designed to assure subject safety and evaluate liver event etiology (in alignment with the FDA premarketing clinical liver safety guidance).

liver chemistry stopping criteria 1-5 are defined below and are presented in a figure in Appendix 2 :

1. ALT \geq 3xULN and bilirubin \geq 2xULN (>35% direct bilirubin) (or ALT \geq 3xULN and INR>1.5, if INR measured)

NOTE: if serum bilirubin fractionation is not immediately available, withdraw study drug for that subject if ALT \geq 3xULN and bilirubin \geq 2xULN. Serum bilirubin fractionation should be performed if testing is available. If testing is unavailable, **record presence of detectable urinary bilirubin on dipstick**, indicating direct bilirubin elevations and suggesting liver injury.

2. ALT \geq 8xULN.
3. ALT \geq 5xULN but <8 xULN persists for \geq 2 weeks

4. ALT \geq 3xULN if associated with symptoms (new or worsening) believed to be related to hepatitis (such as fatigue, nausea, vomiting, right upper quadrant pain or tenderness, or jaundice) or hypersensitivity (such as fever, rash or eosinophilia).
5. ALT \geq 5xULN but $<$ 8 xULN and cannot be monitored weekly for \geq 2 weeks

When any of the liver chemistry stopping criteria 1-5 is met, do the following:

- **Immediately** withdraw investigational product for that subject
- Report the event to GSK **within 24 hours** of learning its occurrence
- Complete the liver event CRF and SAE data collection tool if the event also meets the criteria for an SAE. All events of ALT \geq 3xULN **and** bilirubin \geq 2xULN ($>$ 35% direct) (or ALT \geq 3xULN **and** INR $>$ 1.5, if INR measured); INR measurement is not required and the threshold value stated will not apply to patients receiving anticoagulants), termed 'Hy's Law', **must be reported as an SAE (excluding studies of hepatic impairment or cirrhosis).**

NOTE: if serum bilirubin fractionation is not immediately available, withdraw study drug for that subject if ALT \geq 3xULN **and** bilirubin \geq 2xULN. Serum bilirubin fractionation should be performed if testing is available. If testing is unavailable, **record presence of detectable urinary bilirubin on dipstick**, indicating direct bilirubin elevations and suggesting liver injury.

- Complete the liver imaging and/or liver biopsy CRFs if these tests are performed

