- g. All events of possible drug-induced liver injury with hyperbilirubinaemia defined as ALT \geq 3xULN **and** bilirubin \geq 2xULN (>35% direct) (or ALT \geq 3xULN and INR>1.5, if INR measured) termed 'Hy's Law' events (INR measurement is not required and the threshold value stated will not apply to patients receiving anticoagulants).

NOTE: bilirubin fractionation is performed if testing is available. If testing is unavailable, record presence of detectable urinary bilirubin on dipstick indicating direct bilirubin elevations and suggesting liver injury. If testing is unavailable and a subject meets the criterion of total bilirubin \geq 2xULN, then the event is still reported as an SAE. If INR is obtained, include values on the SAE form. INR elevations >1.5 suggest severe liver injury.

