
 • Subjects falling into the following categories will be summarised: 
 ○ ALT ≥3xULN and Total Bilirubin ≥2xULN ○ ALT ≥3xULN and INR >1.5xULN ○ Hepatocellular injury ○ Hepatocellular injury and Total Bilirubin ≥2xULN ○ ALT ≥3xULN, ≥5xULN, ≥8xULN, ≥10xULN, ≥20xULN, ○ Total Bilirubin ≥2xULN ○ ALP ≥2xULN and (Baseline ALP <2xULN or Baseline ALP missing) • Time from first dose of study treatment to first ALT elevation ≥3x (ULN) (days) will be calculated as: $(\text{Date of first ALT } \geq 3\text{xULN}) - (\text{Date of first dose})$ • Further details can be found in the IDSL core standards 'Liver Event Displays'.

Vital Signs
Potential Clinical Importance (PCI)

 The categories for PCI criteria are: Low; Normal; High. Data will be summarised by nominal visit, but will also include 'any on-therapy visit' and 'any post-baseline visit' categories. These 'any visit' categories will also include unscheduled visits. The data is summarised using a shift table, comparing the baseline category to the worst case post-baseline category at that time-point (note, worst-case is applicable for the 'any visit' categories). The percentages are based on the number of subjects in the treatment group with data for the test post-baseline at that time-point. Subjects with missing baseline value are to be assumed to have normal/within range baseline value. Worst case can be either High or Low. If a subject has both a decrease 'Low' and an increase 'High', then the subject is counted in both the 'Low' and 'High' categories.

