3.38.	Safety		Summary Characteristics of On-therapy Investigator-Reported Injection Site Reactions by Anti-Albiglutide Antibody Status		SAC [1]
3.39.	Safety	AE1	Summary of On-therapy Investigator-Reported Systemic Allergic Reactions by SOC and PT		SAC [1]
3.40.	Safety		Summary of On-therapy Investigator-Reported Renal Impairment by SOC and PT		SAC [1]
3.41.	Safety		Summary of On-therapy Diabetic Ketoacidosis (DKA) identified by a Customised MedDRA Query by SOC and PT		SAC [1]
3.42.	Safety		Summary of On-therapy Appendicitis identified from a Customised MedDRA Query by SOC and PT		SAC [1]
3.43.	Safety		Summary of On-therapy Malignant Neoplasms identified from a Standard MedDRA Query by SOC and PT		SAC [1]
3.44.	Safety		Summary of On-therapy Liver Events identified from a Customised MedDRA Query by SOC and PT		SAC[1]
Laboratory: Chemistry					
3.45.	Safety	LB1	Summary of Chemistry Changes from Baseline by Visit	ICH E3	SAC [1]
3.46.	Safety	LB17	Summary of Chemistry Shifts from Baseline with Respect to Potential Clinical Importance (PCI) Criteria	ICH E3	SAC [1]

Safety : Tables					
No.	Population	IDSL / TST ID / Example Shell	Title	Programming Notes	Deliverable [Priority]
Laboratory: Hematology					
3.47.	Safety	LB1	Summary of Hematology Changes from Baseline by Visit	ICH E3	SAC [1]
3.48.	Safety	LB17	Summary of Hematology Shifts from Baseline with Respect to Potential Clinical Importance (PCI) Criteria	ICH E3	SAC [1]
Laboratory: Urinalysis					
3.49.	Safety	LB1	Summary of Urinalysis Changes from Baseline by Visit	ICH E3	SAC [1]
3.50.	Safety	UR3	Summary of Urinalysis Categorical Results	IDSL	SAC [1]
Laboratory: Hepatobiliary (Liver)					
3.51.	Safety	LIVER1	Summary of Liver Monitoring/Stopping Event Reporting	IDSL	SAC [1]
3.52.	Safety	LIVER10	Summary of Hepatobiliary Laboratory Abnormalities	IDSL	SAC [1]
ECG					
3.53.	Safety	EG1, GLP113121, Switch	Summary of ECG Findings by Visit	IDSL	SAC [1]
3.54.	Safety	EG2, per vitals/lab templates	Summary of ECG Changes from Baseline by Visit	IDSL	SAC [1]
3.55.	Safety	per vitals/lab templates	Summary of ECG Shifts from Baseline with Respect to Potential Clinical Importance (PCI) Criteria		SAC [1]
3.56.	Safety	CP_EG11, GLP113121, Switch	Summary of QTcB and QTcF ECG Results by Visit and Category	IDSL	SAC [1]

Safety : Tables					
No.	Population	IDSL / TST ID / Example Shell	Title	Programming Notes	Deliverable [Priority]

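### The SAP's ALT/INR liver category multiplies the INR limit by the ULN while the protocol uses an absolute 1.5, so a protocol-defined case could be missing from that row

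*SAP*

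**What the plan says.** **SAP.** Section 11.5.3 (Hepatotoxicity) lists the categories to be summarised. One is "ALT ≥3xULN and INR >1.5xULN". Another set in the same list is "ALT ≥3xULN, ≥5xULN, ≥8xULN, ≥10xULN, ≥20xULN", so raised ALT alone has its own rows. The list feeds Table 3.52, titled "Summary of Hepatobiliary Laboratory Abnormalities". Section 8.2.2.2 adds a listing of the subjects who met each criterion after baseline, which is Listing 75. Sections 8.2.2.1 and 11.5.3 restrict laboratory tables, figures and listings to central-laboratory data.

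**Protocol.** Liver stopping criterion 1 in section 6.4.9 has a bilirubin limb and an INR limb. The INR limb is ALT at or above "3xULN and INR>1.5, if INR measured". The same absolute limit appears in item g of the SAE definition (section 6.4.10.2), whose note adds "INR elevations >1.5 suggest severe liver injury", and in the prompt-reporting table of section 6.4.23. When a stopping criterion is met, the site is told to "withdraw investigational product for that subject" immediately, and events meeting criterion 1 must be reported as SAEs. Section 6.4.9 also states "INR measurement is not required and the threshold value stated will not apply to patients receiving anticoagulants".

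**The concern.** The protocol's limit is a fixed INR value, while the SAP's limit moves with the laboratory's reference range. With a ULN above 1.0 the SAP cut-off is the higher and less sensitive of the two. A subject could then have treatment withdrawn and an SAE filed on the INR limb, yet not be counted in the row that corresponds to that limb.

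What is at stake is agreement between outputs. Table 3.51 takes liver stopping events from the eCRF, as the protocol defines them. Table 3.52 follows it directly and takes its counts from laboratory values. A reader who compares the two could find a criterion 1 event in one with no matching ALT/INR entry in the other. Protocol section 1.3.1 names hepatotoxicity as a potential risk on the strength of one probable case in the Phase III programme, so the classification of a single subject would be noticed.

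**Working it through.** No sample size, power or error rate depends on this point. The check compares the two texts and adds one line of arithmetic.

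**Inputs**
- Protocol limit: INR above 1.5 (sections 6.4.9, 6.4.10.2 and 6.4.23).
- SAP limit: INR above 1.5 × ULN (section 11.5.3).
- INR ULN: not given in either document; assumed to lie between 1.0 and 1.3.

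**Formula**

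SAP cut-off = 1.5 × ULN. The row misses INR values above 1.5 and up to 1.5 × ULN.

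| Assumed INR ULN | SAP cut-off | INR values that meet the protocol limit but not the SAP row |
|---|---|---|
| 1.0 | 1.5 × 1.0 = 1.50 | none |
| 1.1 | 1.5 × 1.1 = 1.65 | above 1.5, up to 1.65 |
| 1.2 | 1.5 × 1.2 = 1.80 | above 1.5, up to 1.80 |
| 1.3 | 1.5 × 1.3 = 1.95 | above 1.5, up to 1.95 |

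**Example, with an assumed ULN of 1.2.** Take a subject with ALT 4xULN, INR 1.6 and bilirubin below 2xULN, not on anticoagulants.
- Protocol criterion 1: 4 ≥ 3 and 1.6 > 1.5, so it is met through INR.
- SAP ALT/INR row: 1.6 < 1.80, so the subject is not counted.
- SAP ALT/bilirubin row: bilirubin is below 2xULN, so the subject is not counted.
- SAP row for ALT at or above 3xULN: 4 ≥ 3, so the subject is counted.

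**Comparison with the bilirubin row.** The protocol's bilirubin limb also requires more than 35% direct bilirubin, which the SAP row omits. That makes the SAP row broader, and it cannot lose a protocol case. The INR row departs in the other direction whenever the ULN is above 1.0.

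**How often an INR would be available.** INR is optional. It is not in the scheduled panels (protocol section 6.4.7) or among the liver event follow-up tests in section 6.4.9. An INR measured at a local hospital would be excluded from the row under either cut-off, because only central-laboratory data are tabulated.

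**The case against.** The strongest reply is that little turns on this. Any subject on the INR limb has ALT at or above 3xULN, and so is already in the same table. Withdrawal and SAE reporting follow the protocol and do not depend on an SAP category. The event should appear in Table 3.51 and its listing (Listing 58), in the SAE tables (3.13 and 3.15) and in the SAE listings (41 and 42). The SAP also refers to a company display standard for liver events. That standard is not available here, so 1.5 × ULN may be the standard display and not a slip. The table does not claim to reproduce the protocol's Hy's Law definition, and the bilirubin row departs from it too.

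Most of this stands, and it rules out three stronger readings that a reader might infer:
- **That the case would be absent from the table.** It would be absent from one row only.
- **That drug-induced liver injury would be understated overall.** The stopping-event and SAE outputs use the protocol's rule and should show the case.
- **That SAP Table 1 should have declared the change.** Table 1 covers changes to analyses planned in the protocol. Protocol section 8.3.5.4 defines no hepatobiliary table or INR category and leaves further detail to the analysis plan.

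What the reply does not remove is the difference between the two limits, or the fact that the ALT/INR row can omit a subject whom the protocol would place there. A company standard may explain the wording, but the SAP gives no reason for a different limit in this trial.

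**Conclusion.** The mismatch is real and minor. If the INR ULN is above 1.0, a protocol-defined ALT/INR case could be missing from the ALT/INR row of Table 3.52. It would presumably be missing from Listing 75 too, since no separate criteria are given for that listing. The size rests on an assumed ULN: at 1.0 the rules coincide, and at 1.3 the gap runs from 1.5 to 1.95. Few or no subjects are likely to be affected, because INR is optional and unscheduled and a local result would not be tabulated anyway. The statement that the subject still counts in the ALT row assumes that the raised ALT came from the central laboratory. No efficacy result, design feature or subject's management is affected. The point concerns consistency between the two documents and takes no view on which INR limit is clinically right.

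**What to change.** - Reconcile the category in SAP section 11.5.3, and with it Table 3.52 and Listing 75, with the protocol's stated definition: ALT at or above "3xULN and INR>1.5, if INR measured". The protocol's exception for subjects on anticoagulants should be carried over in a footnote. If the ULN-based limit is kept on purpose, the SAP should say so and give the reason.
- Allow INR values recorded from local laboratories to count for this row, flagged by source, as a stated exception to the central-laboratory-only rule in SAP sections 8.2.2.1 and 11.5.3. Without this, changing the threshold would not bring a locally measured INR into the row. The values should be on file: protocol section 6.4.7 requires local results that change management to be recorded in the CRF, and section 6.4.10.2 asks for INR values on the SAE form.

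The cost is one threshold, one sentence on data source and a small programming change, best made before unblinding. No new data collection is needed.

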11.5.4. Efficacy

Mixed Meal Tolerance Test (MMTT) Efficacy Endpoints
Stimulated (from MMTT) 2 hour plasma C-peptide AUC

 The C-peptide measurements collected during the 120 minute period following a MMTT are referred to as stimulated C-peptide values. Mixed meal stimulated C-peptide AUC is the area under the C-peptide/time curve from Time 0 to 120 minutes, calculated using the trapezoidal rule. In the computation of the AUC, time will be the nominal sampling time, which will be assigned based on the corresponding visit label in the laboratory results dataset. This reported AUC is normalized for time interval by dividing it by 120 minutes. Note, 120 minutes is used if the result at t=120 is non-missing, otherwise the time difference between first and last times with non-missing results is used. This normalized AUC will be calculated for each subject at Baseline, week 16, week 28, week 52 and week 64. Throughout this document, the term 'C-peptide AUC' refers to time normalized mixed-meal stimulated C-peptide AUC (note: this is equivalent to a weighted mean AUC). Time normalized AUC(0-2H)/weighted mean AUC(0-2H) will be derived for C-peptide and Glucagon Note: time point refers to the nominal sampling time from laboratory data. The weighted mean parameters will be derived by calculating the area under the curve AUC using the trapezoidal rule, and then dividing by the nominal relevant time interval (i.e. $tf - tl$): Weighted Mean $(tf - tl) = \left[\frac{1}{2} \sum_{i=1}^{I-1} (t_{i+1} - t_i)(y_i + y_{i+1}) \right] / [tl - tf]$ Where: y_i = Value of endpoint at ith time point t_i = The ith nominal time point (mins) for MMTT: Before MMTT : $t1=0$ After MMTT : $t2 = 15m, t3 = 30m, t4=60m, t5=90m, t6=120m$ tf = Nominal time point (hrs) of first non-missing obs (in planned time $tf=0h$) tl = Nominal time point (hrs) of last non-missing obs (e.g. in planned time for Glucose, $tl=120m$) I = Number of time points used in the AUC calculation (e.g. $I=6$) If one or more of these assessments is missing (note: values reported as BLQ are not

Mixed Meal Tolerance Test (MMTT) Efficacy Endpoints

considered missing), AUCs will be calculated based on the non-missing data using the trapezoidal rule. If the Time 0 assessment is missing, it will be substituted with the value from the -10 minute time point. For an AUC to be calculated, there must be a minimum of one fasting data point (assessments scheduled for -10 minutes and Time 0), and one post-mixed meal data point (assessments scheduled for 15, 30, 60, 90, and 120 minutes). If this minimum number of data points is not available, the AUC will be recorded as missing.

- If the MMTT is conducted when the plasma glucose values are out of the range specified, the data will not be included in the analysis and treated as missing. Prior to the MMTT, plasma glucose will be measured using a finger-stick test and must be > 3.9 mmol/L (70 mg/dL) and ≤ 11.1 mmol/L (200 mg/dL) for the data to be included in the analysis. Only the plasma glucose values from the finger-stick test will be used to exclude data from the analysis (no other glucose values will be considered). The MMTT will be treated as missing in the summary/analyses, but will be provided in data listings (along with finger-stick test results).
- Finger-stick glucose results can be identified in the SDTM.LB dataset using LBTEST='Glucose' and VISIT ne " and LBNAM='NOT APPLICABLE - NO RANGES EXPECTED', LBTPT=' ' and LBSPEC='BLOOD'.

Maximum Stimulated C-peptide

- This will be derived as the highest C-peptide value at any time point during the 2 hour MMTT after the subject has ingested the mixed meal.

Plasma Glucagon AUC (0-2hrs)

- This will be calculated as described for C-peptide AUC, but using the plasma glucagon measurements.
- Calculated using nominal times only.
- Change from baseline in plasma glucagon AUC (from MMTT) is a secondary endpoint. The lower limit of quantification (LLQ) for the glucagon test at study start was 0.0378 nmol/l (SI: 134.043 ng/l), but during the study this lower limit was changed to 0.0223 nmol/l (SI: 79.078 ng/l). All samples received by Q2 on or after 29th August 2015 have a lower limit of 0.0223, whereas any samples received before 29th August have a lower limit of 0.0378. A large proportion of results were reported as <LLQ (i.e. <0.0378 or <0.0223). At a subject level, if this changed mid-way through the study for an individual subject then there could be an artificial lowering of the plasma glucagon value due to the change in limit of quantification rather than any treatment effect (for example, if AUC at baseline was based on <0.0378 and at week 28 on <0.0223). For such subjects, the data is un-interpretable. The following rules will be implemented to account for this:
 - Following a review of the data, the lower limit of quantification used for a sample will be assigned as: samples dated after 20th August 2015 used a lower limit of 0.0223; samples dated on or before 20th August 2015 used a lower limit of 0.0378.
 - For subjects who have data assessed using the same lower limit throughout the study (either 0.0378 or 0.0223) then no changes will be made and the data will be used as recorded.
 - For subjects who have baseline data recorded using the 0.0378 limit, but data for subsequent visits reported using the 0.0223 limit, then all data will be used as if reported using the original

Mixed Meal Tolerance Test (MMTT) Efficacy Endpoints

limit of 0.0378.

- For visits using the original limit of 0.0378, data will be used as recorded.
- For visits using the updated 0.0223 limit, any results reported with a value <0.0378 (either a numeric value between 0.0223 and 0.0378, or a value reported as <0.0223) will be changed so the data used is included as <0.0378. Any results with a value \geq 0.0378 will remain unchanged.
- Although described in terms of original units here, data will be summarised using SI units.

Other Efficacy Endpoints

HbA1c

- HbA1c will be summarised as reported from the central laboratory with units as % of total haemoglobin.
- In addition, summary statistics will be produced for HbA1c with units of mmol/mol.
- For HbA1c measured in mmol/mol, values can be converted to % based on the following [Geistanger, 2008; Hoelzel, 2004]:

$$\text{HbA1c (\%)} = [0.09148 * \text{HbA1c (mmol/mol)}] + 2.152$$
- Therefore, for HbA1c measured in %, values will be converted to mmol/mol based on solving the above equation as follows:

$$\text{HbA1c (mmol/mol)} = [\text{HbA1c (\%)} - 2.152] / 0.09148$$

Exogenous Insulin Use (Mean Daily Insulin Use)

- Mean Daily Insulin Use
- In a change to the planned derivation specified in the protocol:
- In this section, the term “mean daily insulin use” will refer to mean total daily insulin dose per kg body weight. The mean total daily insulin dose per kg body weight will be computer as the sum of average prandial insulin doses and average of basal insulin doses for each subject recorded daily for the three days prior to the specified visits, divided by the subject’s body weight in kg, using the most recently obtained weight measurement.
- Subjects will record their daily insulin use in an electronic diary. This information will be transferred to the concomitant medications dataset. Insulin usage is made up of two types – long-acting (basal) and meal-time (prandial) insulin. Both types will be included when calculating daily insulin usage. Data will be identified using the variable CMTYPCD ('192'=Long-acting insulin and '193'=Meal-time insulin).
- This information will be collected for at least 3 days before Baseline, daily for the first 2 weeks and for at least 3 days preceding the telephone calls/visits at Week 3 through to Week 16, Week 22, Week 28, Week 34, Week 40, Week 46, Week 52 and Week 64. Only data at Baseline, Week 4, 8, 16, 28, 40, 52 and 64 will be included in summary tables and analyses. Data from all time points will be listed.
- Only data from the 3 days immediately preceding the study visit will be used in calculation of mean daily insulin, even if more than 3 days of data are recorded. See Section 11.2.2.
- A subject’s mean daily insulin use will be calculated as follows:
- Mean total daily insulin use (units/kg/day) = (Average long-acting insulin over the 3 consecutive days + average meal-time insulin over the 3 consecutive days)/body weight (kg)
- Calculations at each time point will use the most recently obtained weight. To select the most

Other Efficacy Endpoints

- recently obtained weight for adjustment of mean total daily insulin dose at a visit, measurements up to and including the visit are considered.
- For calculations of the average meal-time insulin (prandial):
 - a subject must have non-missing insulin doses (i.e., dose of 0 or above) for breakfast, lunch and dinner for a day to be included in the calculations.
 - It is the total meal-time insulin for each day that is used in calculations.
- For calculations of the average long-acting insulin (basal):
 - For a day to be included in the calculations, a subject must have at least one non-missing long acting insulin dose (0 mg dose counts as non-missing, as the subject has confirmed no dose). If a day has any missing doses of long-acting insulin recorded then it will not be included in the calculations, even if it also has non-missing doses recorded.
- The evaluability of data from each of the 3 days is defined separately for average meal-time insulin and average long-acting insulin. The average for each insulin parameter is then calculated using only data from the evaluable days and using the number of evaluable days, for each insulin parameter respectively.
- The average total daily insulin dose will be the sum of the average meal-time insulin and the average long-acting insulin at each visit. If either the average mealtime insulin or the average long-acting insulin is unevaluable then the total daily insulin will be unevaluable.
- This total will then be adjusted by dividing by the most recent body weight (kg)

Responders

- A subject will be considered a responder if, at a given visit, the subject has:
 - $\text{HbA1c} \leq 7.0\%$ and
 - Mean daily insulin use $< 0.5 \text{ units/kg/day}$.
- HbA1c and mean daily insulin use will be calculated as described above, and values compared at each time point of interest (Week 4, 8, 16, 28, 40, 52 and 64) to determine if a subject is classed as a responder or not

Partial Remission Status

- A subject achieving partial remission status is defined as a subject with Insulin Dose Adjusted A1c (IDAA1C) ≤ 9.0 [Mortensen, 2009].
- Insulin-dose adjusted A1c (IDAA1c) is a composite variable, which is a weighted sum of insulin use and HbA1c level.
- IDAA1C is calculated as:
 - $\text{HbA1c}(\%) + 4 \times \{\text{mean daily insulin use per kg body weight (IU/kg)}\}$
 - where the computation of mean total daily insulin use per kg body weight is as described above
- The calculated IDAA1C value will be rounded to 2 decimal places before assigning partial remission status. Therefore the largest value assigned as ≤ 9.0 would be 9.004999.

Subject-Reported Hypoglycaemic Events (Efficacy)

- Subject-reported hypoglycaemic event data collection and derivation is described in Section 11.5.3
- Significant hypoglycaemia is defined as events with plasma glucose $\leq 3.9 \text{ mmol/L} (\leq 70 \text{ mg/dL})$ and/or requiring third party intervention. This corresponds to ADA category definitions of severe hypoglycaemia, documented symptomatic hypoglycaemia and asymptomatic hypoglycaemia.
- Events will be assigned to time periods based on the date of event:

Other Efficacy Endpoints

 Baseline to Week 24: study day 1 to study day 168 >Week 24 to ≤Week 52: study day 169 to study day 364 The number of significant hypoglycaemic events that each subject experienced in each time period will be calculated.
7 point Glucose Profile

 Data from the 7-point blood glucose profile page in the eCRF will be used for this endpoint. Data recorded from the glucose meter to the electronic diary will not be used. The schedules collection times for the 7-point glucose profile are: before breakfast (at least 8 hours without food intake); 2 hours after breakfast; before lunch; 2 hours after lunch; before dinner; 2 hours after dinner; at bedtime. Glucose will be presented in mmol/L. A glucose value reported in mg/dL will be converted to mmol/L by multiplying the value by 0.05551. The 7-point glucose profile will be assessed at Baseline, Week 28 and Week 52. All non-missing data will be included in the summaries of glucose levels at each of the 7 specified time-points (before breakfast, 2 h after breakfast, etc.). To be evaluable for the endpoints relating to number and magnitude of hypo/hyperglycaemic excursions (endpoints detailed below) the following rules will apply: 
 A subject with non-missing glucose values for at least 4 of the 7 scheduled time-points will be evaluable for hypoglycaemic excursions and hyperglycaemic excursions A subject with <4 non-missing glucose values will be evaluable for hypoglycaemic excursions only if one or more of the non-missing glucose values is a hypoglycaemic excursion (i.e., blood glucose level is ≤3.9 mmol/L) A subject with <4 non-missing glucose values will be evaluable for hyperglycaemic excursions only if one or more of the non-missing glucose values is a hyperglycaemic excursion (i.e., blood glucose level is >10.0 mmol/L) Subjects will be determined as evaluable for hypoglycaemic excursions and hyperglycaemic excursions separately at each visit, based on the non-missing data reported at that visit. At Baseline, Week 28 and Week 52, the following parameters will be calculated for each subject: 
 Hypoglycaemic Excursions: A hypoglycaemic excursion is defined as an occurrence where the blood glucose level is ≤3.9 mmol/L (i.e. ≤70 mg/dL) Any hypoglycaemic excursions (yes/no) Number of hypoglycaemic excursions (e.g. expected 0 -7) Greatest hypoglycaemic excursion: this will be calculated as 3.9 mmol/L minus the lowest recorded glucose level during the 7-point glucose profile. If a subject has data recorded in the interval, but does not have a value ≤3.9 mmol/L, the subject's greatest hypoglycaemic excursion for that interval would be 0 mmol/L. Hyperglycaemic Excursions: A hyperglycaemic excursion is defined as an occurrence where the blood glucose level is >10.0 mmol/L (i.e. >180 mg/dL) Any hyperglycaemic excursions (yes/no) Number of hyperglycaemic excursions (e.g. expected 0 -7) Greatest hyperglycaemic excursion: this will be calculated as the largest recorded glucose level during the 7-point glucose profile minus 10.0 mmol/L. If a subject has data recorded in the

Other Efficacy Endpoints	
	interval, but does not have a value $>10.0 \text{ mmol/L}$, the subject's greatest hyperglycaemic excursion for that interval would be 0 mmol/L.
72 hour CGM	

 Glucose variability is also assessed using continuous glucose monitoring (CGM), where glucose is sampled every 5 mins for 72 hours. 72-hour CGM will be performed at baseline, week 28 and week 52. At each time point the following parameters will be calculated for each subject: 
 Time spent with a plasma glucose $\leq 3.9 \text{ mmol/L}$ Time spent with a plasma glucose between >3.9 and 10.0 mmol/L Time spent with a plasma glucose $>10.0 \text{ mmol/L}$ Data will be derived as follows: A subject must have at least 24 hours of CGM data recorded in order to be considered evaluable (note, this does not need to be in one continuous period) If a value of x is recorded at time 0, a value of y at time 5 mins, and a value of z at time 10 mins then a subject will be considered to have a plasma glucose level of x from time 0-5 (5mins); a value of y from time 5-10 (5mins); a value of z from time 10-15 (5mins); etc. Each 5 minute time period will be assigned to time spent $\leq 3.9 \text{ mmol/L}$, between >3.9 and 10.0 mmol/L and $>10.0 \text{ mmol/L}$. Data for each subject will be summed into the 3 categories, over the time period they have available, so they have: 
 Actual time spent $\leq 3.9 \text{ mmol/L}$, Actual time spent between >3.9 and 10.0 mmol/L Actual time spent $>10.0 \text{ mmol/L}$. Total actual time To calculate the actual time spent within each range, each CGM observation will be assigned as $\leq 3.9 \text{ mmol/L}$, between >3.9 and 10.0 mmol/L, and $>10.0 \text{ mmol/L}$. The number of observations within each range will be summed, and the total number of observations within each range will be multiplied by 5 minutes to calculate the actual time within each range. The total actual time is the sum of the actual time spent within each range for the 3 ranges. There may be periods of missing data within the 72h CGM. As it is unknown what the plasma glucose value was during these times, they will be excluded from calculations. 	
For each category, data will be converted into time spent for a 24 hour period as follows:	

 Time spent $\leq 3.9 \text{ mmol/L}$ (hours/24h) = Actual time spent $\leq 3.9 \text{ mmol/L}$ / Total actual time * 24 Time spent between >3.9 and 10.0 mmol/L (hours/24h) = Actual time spent between >3.9 and 10.0 mmol/L / Total actual time * 24 Time spent $>10.0 \text{ mmol/L}$ (hours/24h) = Actual time spent $>10.0 \text{ mmol/L}$ / Total actual time * 24 The time spent in each of the 3 glycaemic state for a 24h period should sum to 24h for each subject. For each category, change from baseline will be calculated using the time spent for a 24 hour period (hours/24h) In addition, the time spent in each of the 3 glycaemic states will be calculated as a percentage e.g. 	
Time spent $\leq 3.9 \text{ mmol/L}$ (hours/24h) = Actual time spent $\leq 3.9 \text{ mmol/L}$ / Total actual time * 100	

